## 5.3 PER PROTOCOL [PP] POPULATION

Immunogenicity will be assessed only in Phase 3 subjects who are randomized at the Ben Luc site. All such subjects in the Full Analysis population who have valid post-vaccination immunogenicity measures with no major protocol violations that are determined to potentially interfere with the immunogenicity assessment of the study vaccine will be included. This population will serve as the primary analysis population for all immunogenicity objectives.

The criteria for exclusion of subjects from the Per Protocol Population will be established before breaking the blind and will be based on the blinded review of protocol violations, which will be identified and categorized as described in [Appendix 1](#).

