## 6. GENERAL CONSIDERATIONS

By-subject data listings, summary tables, figures and statistical tests will be performed using SAS® Version 9.4 or higher.

All clinical data, including laboratory and clinical data from an internal database will be provided as raw datasets. CDISC SDTM 3.2 compliant SAS datasets will then be generated. Coding of AEs and current medical conditions will be included in the SDTM datasets.

Appropriate SAS programs will be prepared and validated according to QuintilesIMS standard operating procedures.

The following descriptive statistics will be presented in summary tables:

- Continuous variables: Number (observed cases), mean, median, standard deviation (SD), minimum, and maximum

---

Document:	\\EEDC-NAS01A\Biosdata\Path\IVACFLU-S\IYA06804\Biostatistics		
	Documentation\SAP\IVACFLU-S-0203_SAP_Draft v1.0		
Author:	[name]	Version Number:	1.0
		Version Date:	[11AUG2017]
Template No:	CS_TP_BS016 Revision 4	Reference:	CS_WI_BS005
Effective Date:	01Apr2016		

- Categorical variables: Summarized by treatment group using frequency tables (frequency [n] and percentage [%]). Percentages will be calculated relative to the total number of subjects in the relevant analysis set with data available, if not otherwise specified.

Two-sided exact 95% confidence intervals (CIs) will be presented unless otherwise specified.

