### Protocol Deviation Classifications

Categories	Severity

 
• Informed consent
 
• Eligibility and Entry Criteria
 
• Concomitant Medication Criteria
 
• Study Procedures Criteria
 
• Serious Adverse Event Criteria
 
• Randomization Criteria
 
• Visit Schedule Criteria
 
• Administrative Criteria
 
• Source Document Criteria
 
• RA or CEC Approvals Criteria
 
• IP Compliance
 
• Other Criteria
 
	
 
• Minor Deviations from accepted procedures that will not adversely affect subject/data, but should be dealt with appropriately.
 
• Major Protocol Deviation Issues that impact upon scientific, ethical, regulatory or business integrity and which, if left unattended could become critical. Such issues require timely action.
 
• Critical Protocol Deviation Issues that threaten scientific, ethical, regulatory or business integrity and could invalidate acceptability of a study (or part of it) to a customer or regulatory body, or invoke regulatory action which require immediate attention.
 

**Critical** deviations include, but are not limited to:

- Eligibility and entry criteria: subject was enrolled even though entry criteria were not satisfied
- Subject did not sign ICF yet was enrolled into the study
- Any study procedures on S1 day were done prior to consent being signed

**Major** deviations include, but are not limited to:

- Incorrect study product assigned and administered according to randomization
- Incorrect version of signed ICF (not currently approved version)
- ICF was not signed by either investigator or study participant
- IP temperature excursion (important deviation if IP is not allowed to be used, minor deviation if IP is allowed to be used)
- Subject does not complete more than 50% of subject diary card
- Subject visit (D8, D22, D91) is not completed or not done Use of prohibited drugs during study period
- SAE not reported according to protocol requirement
- Immunological sample is not collected as per protocol requirement (collected sample which cannot be analyzed is not considered as a deviation)
- Loss of source documents

**Minor** deviations include, but are not limited to:

- Subject visit is outside of visit window
- Incomplete source documents
- Procedures carried out by staff not delegated in the delegation log

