 Summary of Concomitant Medications  
 Full Analysis Population

Age Group: <Overall> <18-45> <46-60>

Reported Term	Vaccine (N=XX) n (%)	Placebo (N=XX) n (%)	Total (N=XX) n (%)
Number of Subjects With at Least One Medication	xx (xx.x)	xx (xx.x)	xx (xx.x)
Reported Term 1	xx (xx.x)	xx (xx.x)	xx (xx.x)
Reported Term 2	xx (xx.x)	xx (xx.x)	xx (xx.x)
...			

Data is based on the combined phases 2 and 3, pooled across study sites.  
 N= Total number of subjects in the relevant population per by-group stratification level, n= Number of subjects in each category, % = Calculated relative to the total number of subjects in the relevant population  
 Subjects with multiple usage of the same medication within the same reported term were counted only once.  
 Concomitant medication: Defined as medication started on or after the day of vaccination or were ongoing on the date of vaccination or ended on or after the vaccination  
 Source Data: Listing 16.2.4.3

Programming Note: Sorted by alphabetical order of Reported term.

Document:	\\EEDC-NAS01A\Biosdata\Path\IVACFLU-S\IYA06804\Biostatistics \Documentation\SAP\IVACFLU-S-0203_Mock_Tables_V1.0		
Author:	[name]	Version Number:	1.0
		Version Date:	11AUG 2017
Template No:	CS_TP_BS016 Revision 4	Reference:	CS_WI_BS005
Effective Date:	01Apr2016		

TABLE AND LISTING MOCK SHELL

Table 14.2.1.1  
 Seroconversion and 95% Confidence Intervals for the Hemagglutination Inhibition (HAI) Titers by Age group  
 Per-protocol population

Age Group: <Overall> <18-45> <46-60>	Titers	Criteria	Day	Vaccine (N=xx)	Placebo (N=xx)
A/H1N1	Seroconversion	n	Day 22	xx	xx
		n/N(%)		xx.x	xx.x
		95% CI		[xx.xx, xx.xx]	[xx.xx, xx.xx]
A/H3N2					
B					

Sera samples were collected in phase 3 study at one site (Ben Luc).  
 N= Total number of subjects in each agegroup, n= Total number of subjects meeting the event, CI= Confidence Interval  
 Percentages were based on the total number of subjects in each vaccine group (N).  
 95% confidence interval for single proportion is calculated using Exact Clopper-Pearson method.  
 Seroconversion is defined as a serum HAI antibody titer meeting the following criteria:  
 Pre-vaccination titer <1:10 and a post-vaccination titer measured on Day 22 of ≥1:40 or Pre-vaccination titer ≥1:10 and at least a four-fold increase in post vaccination measured on Day 22  
 Source: Listing 16.2.6.1  
 Programming note: Repeat the shell for all the three age groups in the same table.

Table 14.2.1.2  

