**Geometric Mean titer (GMT) for the Hemagglutination Inhibition (HAI) Titers by Age group**  
Per-protocol population

Age Group: <Overall> <18-45> <46-60>

Titers		Day	Vaccine (N=xx)	Placebo (N=xx)
A/H1N1	GMT			
	n	Day 1	xx	xx
	Geometric mean titer		xx.x	xx.x
	Geometric Standard Deviation		xx.x	xx.x
	95% CI		[xx.xx, xx.xx]	[xx.xx, xx.xx]
		Day 22		
A/H3N2				
B				

Sera samples were collected in phase 3 study at one site (Ben Luc).

Notes:

N- Total number of subjects in each agegroup; n - Total number of subjects with the titer measurement.

The confidence intervals were constructed using t distribution.

Pre-vaccination (Day 1) value is considered as baseline.

Source: Listing 16.2.6.1

Programming note: Repeat the shell for all the three age groups in the same table.

Document: \\EEDC-NAS01A\Biosdata\Path\IVACFLU-S\IYA06804\Biostatistics \Documentation\SAP\IVACFLU-S-0203\_Mock\_Tables\_V1.0

Author: [name]

Version Number:

1.0

Version Date:

11AUG 2017]

Template No: CS\_TP\_BS016 Revision 4

Reference: CS\_WI\_BS005

Effective Date: 01Apr2016

Copyright © 2009, 2010, 2012, 2016 Quintiles Transnational Corp. All rights reserved.

The contents of this document are confidential and proprietary to Quintiles Transnational Corp. Unauthorized use, disclosure or reproduction is strictly prohibited.

TABLE AND LISTING MOCK SHELL

Table 14.2.1.6  
Geometric Mean titer (GMT) for the Hemagglutination Inhibition (HAI) Titers by Age group  
Full Analysis population

Same layout as for 14.2.1.5

Table 14.2.1.7  
Geometric Mean Fold Rise (GMFR) for the Hemagglutination Inhibition (HAI) Titers by Age group  
Per-protocol population

Age Group: <Overall> <18-45> <46-60>

Titers		Day	Vaccine (N=xx)	Placebo (N=xx)
A/H1N1	GMFR			
	n	Day 22/Day 1	xx	xx
	Geometric mean fold ratio		xx.x	xx.x
	Geometric Standard Deviation		xx.x	xx.x
	95% CI		[xx.xx, xx.xx]	[xx.xx, xx.xx]
A/H3N2				
B				

Sera samples were collected in phase 3 study at one site (Ben Luc).  
N- Total number of subjects in each agegroup; n - Total number of subjects with the titer measurements at both Day 1 and Day 22.  
The confidence intervals were constructed using paired t-test.  
Pre-vaccination (Day 1) value is considered as baseline.  
Source: Listing 16.2.6.1  
Programming note: Repeat the shell for all the three age groups in the same table.

Table 14.2.1.8  
Geometric Mean Fold Rise (GMFR) for the Hemagglutination Inhibition (HAI) Titers by Age group  
Full Analysis population

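### The seroconversion shell divides by everyone in the group, so a per-protocol participant whose Day 1 serum could not be analysed is scored as a non-seroconverter

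*Combined protocol and SAP*

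**What the plan says.** **Who is in the set.** SAP 5.3 admits Phase 3 Ben Luc subjects as follows: "All such subjects in the Full Analysis population who have valid post-vaccination immunogenicity measures", provided there is no major violation that could interfere with the assessment. A Day 1 titer is not mentioned. On exclusions it says: "The criteria for exclusion of subjects from the Per Protocol Population will be established before breaking the blind", on the basis of a blinded review of violations.

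**What counts as a violation.** Appendix 1 lists an immunological sample that was not collected as a major deviation, then adds: "collected sample which cannot be analyzed is not considered as a deviation".

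**What is divided by what.** Three rules are in play:
- SAP 6, general rule: "Percentages will be calculated relative to the total number of subjects in the relevant analysis set with data available, if not otherwise specified". SAP 7.3 adds that missing immunogenicity data are not imputed.
- Shell Table 14.2.1.1 (seroconversion, per protocol): "N= Total number of subjects in each agegroup, n= Total number of subjects meeting the event, CI= Confidence Interval", and "Percentages were based on the total number of subjects in each vaccine group (N").
- Shell Table 14.2.1.7 (geometric mean fold rise, per protocol), where n is: "Total number of subjects with the titer measurements at both Day 1 and Day 22".

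**Supportive analysis.** SAP 16.2.2 repeats all immunogenicity analyses on the full analysis population, which requires randomization and vaccination but no titer. Shell Tables 14.2.1.2 and 14.2.1.4 reuse the layout of Table 14.2.1.3, which has the same footnote on N.

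**The concern.** Seroconversion is a paired outcome: it needs a Day 1 and a Day 22 titer for the same strain. A participant with a good Day 22 titer and an unusable Day 1 serum qualifies for the per-protocol set, and the deviation review has no listed ground for removing that person. The shell's N includes the participant; its n, those meeting the event, cannot. The effect is to score an underivable result as non-response, although SAP 7.3 says nothing is imputed. The fold-rise table leaves the same person out, so two primary parameters rest on different people.

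This matters because protocol 13.8 bases licensure on the point estimate, and SAP 16.1 calls seroconversion the criterion that has most often missed its threshold. A denominator that could be settled either way after the data are seen should not be left open for that endpoint.

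**Working it through.** **1. Who is affected.** From the definition in SAP 16.3:
- Day 1 below 1:10: seroconversion needs Day 22 of at least 1:40.
- Day 1 of 1:10 or more: seroconversion needs a four-fold rise, so Day 22 of at least 4 × 10 = 40.

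A Day 22 titer below 1:40 is therefore non-seroconversion whatever Day 1 was. Only participants at or above 1:40 with no Day 1 titer are undetermined. In Phase 1, 93.3% to 96.7% of vaccinees reached 1:40 by strain (protocol Table 7B), so most affected people would be in this class.

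**2. The plan's own figures.** SAP 16.1.1 uses 100 evaluable vaccinees per age group and binomial responses. Treating strains as independent, with X the number of seroconverters for one strain:
- Age 18–45, true rate 49%, threshold 40%: P(X ≥ 40 | 100, 0.49) = 0.9717; cubed, 0.9175. SAP: 91%.
- Age 46–60, true rate 39%, threshold 30%: P(X ≥ 30 | 100, 0.39) = 0.9759; cubed, 0.9293. SAP: 93%.

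Both reproduce.

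**3. Effect of the denominator.** The serum subset has 210 vaccinees, or 105 per age group. The number of lost Day 1 sera, m, is an assumption. I take the same people as missing for all strains and everyone else as having both titers. The chance of passing all three strains is P(X ≥ r | 105 − m, p)³, where r is the threshold times 105 (shell) or times 105 − m (pairs), rounded up.

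For m = 5:
- Age 18–45, shell: r = 0.40 × 105 = 42; P(X ≥ 42 | 100, 0.49) = 0.9335; cubed, 0.814.
- Age 18–45, pairs: r = 40; 0.9175 as in step 2.
- Age 46–60, shell: r = 0.30 × 105 = 31.5, so 32; P(X ≥ 32 | 100, 0.39) = 0.9395; cubed, 0.829.
- Age 46–60, pairs: r = 30; 0.929.

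The same formula over a range of m:

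| m of 105 | 18–45 at 49%: shell / pairs | 46–60 at 39%: shell / pairs |
|---|---|---|
| 1 | 90.9% / 90.9% | 90.5% / 90.5% |
| 2 | 89.0% / 89.0% | 88.9% / 93.0% |
| 3 | 86.8% / 91.3% | 87.2% / 91.8% |
| 5 | 81.4% / 91.7% | 82.9% / 92.9% |
| 10 | 61.4% / 90.9% | 68.0% / 90.1% |

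Where the columns agree, rounding up gives the same r. At the lowest Phase 1 rate, 76.7%, the probability for m = 5 is about 100% under either rule.

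**4. How much loss would move the expected rate below the threshold.** The fraction is 1 − threshold/rate: 1 − 0.40/0.49 = 18%; 1 − 0.30/0.39 = 23%; 1 − 0.40/0.767 = 48%.

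**5. Full-analysis tables.** SAP 8 confines immunogenicity outputs to the Ben Luc Phase 3 subset. There a vaccinee with no Day 22 titer remains in N for seroprotection as well as seroconversion. If the 5% dropout planned in protocol 4.1 all fell before Day 22, about 5 of 105 would be affected (105 × 0.05 = 5.25). The lowest Phase 1 seroprotection rate, 93.3%, would then show as 93.3% × 100/105 = 88.9%, still well above 70%.

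**The case against.** The best counter-argument is that SAP 6 already answers the question. Its default denominator is subjects with data, SAP 7.3 forbids imputation, and no sentence says a missing Day 1 titer is a failure. The footnote also looks like repeated table text: it recurs in Table 14.2.1.9, which splits results by pre-vaccination titer and where someone without a Day 1 titer fits neither stratum. That supports calling this a conflict between text and shell rather than a deliberate rule. It does not remove the problem: the SAP 6 default yields where something else is specified, the footnote specifies something else, and SAP 8 makes the shells the format and content of the outputs.

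Other points stand and limit the claim:
- A reader might infer that every participant without a Day 1 titer is scored as a failure. That goes too far. An uncollected sample is a major deviation and can lead to exclusion, and a Day 22 titer below 1:40 is a true non-seroconversion.
- A reader might take the plan's 5% allowance as the expected loss of sera. It covers dropout and enrolment overage (protocol 4.1 and 13.2). Protocol 9.2.3 divides each serum into an assay aliquot, two back-ups and an archive remainder, so loss should be uncommon.
- The per-protocol set already requires a post-vaccination measure, so Day 22 seroprotection there is little affected. Table 14.2.1.3 does also report Day 1, where the same footnote applies.

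**Conclusion.** The point holds as a low-severity correction. On its literal wording, the shell for a primary licensure percentage scores a per-protocol participant with Day 22 of at least 1:40 and an unanalysable Day 1 serum as a non-seroconverter, contrary to SAP 6, SAP 7.3 and the fold-rise shell. The full-analysis tables extend this to missing Day 22 titers.

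The size depends on an unknown. With an assumed 5 of 105 sera lost, independent strains and true rates at the plan's margin, the chance of passing falls from about 92% to 81% (age 18–45) or from 93% to 83% (age 46–60). With one lost serum the two rules give the same probability, and at the Phase 1 rate the result is a pass regardless.

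Two stronger conclusions might be drawn, and neither is supported. The documents do not show that the trial is likely to miss the criterion for this reason, because they give no loss rate and expect responses far above threshold. Nor can the footnote produce a false pass: it only lowers the vaccine's estimate.

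**What to change.** Before unblinding, amend SAP 5.3 and 16.2 and the shell footnotes:
- **Seroconversion and four-fold rise:** the denominator is subjects with valid Day 1 and Day 22 titers for that strain, as the fold-rise shell already has it. Show that n in the table.
- **Seroprotection:** the denominator is subjects with a valid titer for that strain at that visit.
- **Full-analysis tables:** apply the same rules within the Ben Luc subset.
- **Optional sensitivity analysis:** count undetermined participants as non-responders. This also restores the few with Day 22 below 1:40 and no Day 1 titer, whom the paired rule drops although their outcome is known.

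The cost is a wording change to the SAP and shells, with no new data. The one drawback is that n will differ slightly by strain and parameter.

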## 6. GENERAL CONSIDERATIONS

By-subject data listings, summary tables, figures and statistical tests will be performed using SAS® Version 9.4 or higher.

All clinical data, including laboratory and clinical data from an internal database will be provided as raw datasets. CDISC SDTM 3.2 compliant SAS datasets will then be generated. Coding of AEs and current medical conditions will be included in the SDTM datasets.

Appropriate SAS programs will be prepared and validated according to QuintilesIMS standard operating procedures.

The following descriptive statistics will be presented in summary tables:

- Continuous variables: Number (observed cases), mean, median, standard deviation (SD), minimum, and maximum

---

Document:	\\EEDC-NAS01A\Biosdata\Path\IVACFLU-S\IYA06804\Biostatistics		
	Documentation\SAP\IVACFLU-S-0203_SAP_Draft v1.0		
Author:	[name]	Version Number:	1.0
		Version Date:	[11AUG2017]
Template No:	CS_TP_BS016 Revision 4	Reference:	CS_WI_BS005
Effective Date:	01Apr2016		

- Categorical variables: Summarized by treatment group using frequency tables (frequency [n] and percentage [%]). Percentages will be calculated relative to the total number of subjects in the relevant analysis set with data available, if not otherwise specified.

Two-sided exact 95% confidence intervals (CIs) will be presented unless otherwise specified.

## 6.1 REFERENCE START DATE AND STUDY DAY

Study day will be calculated relative to the reference start date, and will be used to show start/stop day of assessments and events.

Reference start date is defined as the day of vaccination (Day 1), and will appear in every listing where an assessment date or event date appears.

- If the date of the event is on or after the reference date then:  
Study day = (date of event – reference date) + 1.
- If the date of the event is prior to the reference date then:  
Study day = (date of event – reference date).

For the derivation of study day, time of day will be considered, if applicable.

In the situation where the event date is partial or missing, Study day, and any corresponding durations will appear partial or missing in the listings i.e., Study day or any corresponding durations will not be computed.

## 6.2 BASELINE

Unless otherwise specified, Baseline is defined as the last non-missing measurement taken prior to vaccination start date and time (including unscheduled assessments). In the case where the last non-missing measurement and the reference start date coincide, that measurement will be considered pre-baseline, but Adverse Events (AEs) and medications commencing on the reference start date will be considered post-baseline.

## 6.3 DERIVED TIMEPOINTS

Not applicable.

## 6.4 RETESTS, UNSCHEDULED VISITS AND EARLY TERMINATION DATA

In general, for by-visit summaries, data recorded at the nominal visit will be presented. Unscheduled measurements will not be included in by-visit summaries.

---

Document:	\\IEEDC-NAS01A\Biosdata\Path\IVACFLU-S\IYA06804\Biostatistics		
	Documentation\SAP\IVACFLU-S-0203_SAP_Draft v1.0		
Author:	[name]	Version Number:	1.0
		Version Date:	[11AUG2017]
Template No:	CS_TP_BS016 Revision 4	Reference:	CS_WI_BS005
Effective Date:	01Apr2016		

In the case of a retest (same visit number assigned), the earliest available measurement for that visit will be used for by-visit summaries.

Listings will include scheduled, unscheduled, retest and early termination data.

## 6.5 WINDOWING CONVENTIONS

No visit windowing will be performed for this study.

## 6.6 STATISTICAL TESTS

The default significance level will be 5%, confidence intervals will be 95%, and all tests will be two-sided, unless otherwise specified in the description of the analyses.

## 6.7 COMMON CALCULATIONS

For quantitative measurements, change from Baseline to Visit X will be calculated as:

Test Value at Visit X – Baseline Value

## 6.8 SOFTWARE VERSION

All analyses will be conducted using SAS version 9.4 or higher.

## 7. STATISTICAL CONSIDERATIONS

### 7.1 ADJUSTMENT FOR COVARIATES

No adjustment for covariates will be made.

---

Document:	\\IEEDC-NAS01A\Biosdata\Path\IVACFLU-S\IYA06804\Biostatistics		
	Documentation\SAP\IVACFLU-S-0203_SAP_Draft v1.0		
Author:	[name]	Version Number:	1.0
		Version Date:	[11AUG2017]
Template No:	CS_TP_BS016 Revision 4	Reference:	CS_WI_BS005
Effective Date:	01Apr2016		

## 7.2 MULTICENTER STUDIES

Phase 2 will be conducted at a single site, District Health Center of Ben Luc district in Long An Province. Phase 3 enrollment will be conducted at 2 sites, District Health Center of Ben Luc in Long An province and District Health Center of Long Thanh in Dong Nai province.

The data collected from the two study sites will be pooled together for analyses with the below exceptions:

- Subject disposition summaries will be presented both pooled and separately by study site.
- Immunogenicity measurements and analyses will be conducted only in subjects studied at the Ben Luc site during Phase 3

## 7.3 MISSING DATA

Missing safety and immunogenicity data will not be imputed.

## 7.4 MULTIPLE COMPARISONS/ MULTIPLICITY

No multiplicity adjustment to the Type 1 probability of error, alpha, will be made for the multiple testing of immunogenicity endpoints corresponding to the three vaccine antigens under the intersection-union property. That is, the immune responses to each of the three vaccine antigens induced by IVACFLU-S seasonal trivalent split inactivated influenza vaccine need to meet Vietnam Ministry of Health licensure requirements.

